## Phase II substudy analysis

### *Cytokine array*

To determine the impact of melatonin on patient cytokine levels, a cytokine array will be generated for each patient. Briefly, patients will be divided into two cohorts; those receiving melatonin and those receiving placebo treatment. Following data collection, cytokine expression measurements will be log transformed, and a KS-test will verify normality within each dataset. If confirmed, a one-way anova will assess if any cytokines are significantly affected, followed by a t-test corrected for multiple hypothesis testing (bonferroni) to identify which are significantly affected by melatonin treatment. If failed, a Kruskal–Wallis one-way anova will assess if any cytokines are significantly affected, followed by a Wilcoxon signed-rank test corrected for multiple hypothesis testing (bonferroni) to identify which are significantly affected by melatonin treatment.

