### **Surrogate tests for the phase II substudy**

A subset of 80 patients in both groups will undergo testing for NK cell function and characteristics, blood levels of cytokines, CRP, albumin, and leukocytes. Testing will occur four weeks following surgical resection but prior to commencing the study treatment (baseline) and six months after beginning the study treatment (end point). In addition to venipuncture for measurement of CRP, albumin, and leukocytes, immunological functional assays adapted by [name] lab will be conducted on NK cell activity as well as performing a series of assessments for pro- and anti- inflammatory cytokines.

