#### **ii. Cytokine array**

Includes IL2, IL4, IL6, IL10, IL12, IL15, IFN- $\alpha$ , IFN- $\gamma$ , TNF- $\alpha$ , GM-CSF, TGF- $\beta$ 1, and VEGF in a mix 'n match multi-analyte ELISA array (SAbiosciences, Qiagen). Serum (or plasma) will be obtained from human whole blood through centrifugation (30,000 rpm for 20mins). Human cytokines will be determined by sandwich enzyme-linked immunosorbent assay (ELISA), using the Mix 'n Match multi-analyte ELISA array from SA Biosciences. Briefly, 96-well microtiter plates arrive already coated with capture antibody. Recombinant antigens and patient samples are added to their respective wells and incubated for 2h. Samples are then washed and incubated with detection antibodies for 1h. They are again washed and incubated with Avidin-HRP for 30mins. Following a final wash, they are incubated with development substrate and stop solution and have optical density read at 450nm.

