## NSCLC Adjuvant melatonin RCT

[figure not shown]
we essentially have 100% power to detect this difference i.e. this difference will be incredibly unlikely to be missed due to chance.

*Figure 2: For group rates of 20 % and 5 %, power versus sample size per group for different null rate differences.*

In the third and final graph (Figure 3) if we see an event rate of 20% which is also possible in our population and there is a drop of only 5% we are actually powered to nearly 90% with a population of 640.

*Figure 3: For group rates of 20 % and 15 %, power versus sample size per group for different null rate differences.*

For the phase II sub-study, we are interested in exploring potential mechanisms through which melatonin may be exerting activity. An exploratory pilot analysis of 80 subjects will provide information on what is occurring physiologically and is powered to see a 30% significant shift in NK cell functional activity. In addition, with 40 patients in each group, the expected number with recurrence or mortality is expected to be approximately 16 subjects, allowing for comparison of the NK cell function and biologic markers amongst this subgroup, compared to those without recurrence for both the melatonin and the control groups.

Although sample size calculation represent only rough estimates of the true sample required [79], confidence intervals around the primary endpoint will provide strong inferences into how well powered the trial is. It should be noted that our proposed sample is much larger than any of the previously conducted melatonin/cancer trials for which a statistically significant reduction in mortality was found after only one year. Given the sample size we will accrue, we confidently anticipate that the trial is well powered to address the primary objective without undue use of time and resources. The addition of the mechanistic substudy and trial extension will greatly extend the impact of the trial and potential for strong results to lead to policy shifts and a change in pattern of clinical practice leading to better patient care.

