### *Flow cytometry*

To determine the impact of melatonin on NK cell markers, flow cytometry will be performed. Statistical analysis will be similar to that implemented in the cytokine analysis. Following confirmation of normality (KS-Test), a one-way anova will assess if any markers are significantly affected followed by a t-test corrected for multiple hypothesis testing (bonferroni) to identify which are significantly affected by melatonin treatment. If normality is not identified, a Kruskal–Wallis one-way anova will be performed to assess if any markers are significantly affected, followed by a Wilcoxon signed-rank test corrected for multiple hypothesis testing (bonferroni) to identify which are significantly affected by melatonin treatment.

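### In the biomarker substudy, the KS normality gate and the ANOVA or Kruskal-Wallis step for any affected marker add no protection to the Bonferroni tests, and the non-parametric follow-up is a paired test for independent arms

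*Combined protocol and SAP*

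**What the plan says.** Section 8, under Cytokine array, defines the comparison by treatment: "patients will be divided into two cohorts; those receiving melatonin and those receiving placebo treatment". The stated sequence is:

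1. **Gate.** "cytokine expression measurements will be log transformed, and a KS-test will verify normality within each dataset". The reference mean and SD, any Lilliefors correction, and the meaning of a dataset (per arm, per cytokine, per visit) are not given.
2. **Omnibus.** If normality is confirmed, "a one-way anova will assess if any cytokines are significantly affected"; if not, Kruskal-Wallis takes its place. No factor is named.
3. **Follow-up.** Bonferroni-corrected t-tests, or Bonferroni-corrected Wilcoxon signed-rank tests, identify the affected cytokines.

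The Flow cytometry paragraph repeats this for NK-cell markers: "a one-way anova will assess if any markers are significantly affected".

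Section 7.0 describes an exploratory pilot "with 40 patients in each group". Section 6.5 (ii) lists 12 cytokines. Section 6.5 also schedules testing before treatment starts, four weeks after resection, and again six months into treatment. Section 8 does not say how the baseline value enters the analysis. Section 2.1 places the biomarker work second among the primary objectives.

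**The concern.** The wording asks first whether any marker is affected and then which ones. A one-way ANOVA with two arms does not provide that first answer. Depending on the unstated factor, it either repeats the later test or tests something other than a melatonin effect. The normality gate decides which branch is used, but in its ordinary form it has little ability to detect non-normality at this sample size.

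Two things are at stake. A global statement that melatonin affects some cytokine or NK marker could rest on a test that is often positive without any effect. If the omnibus result decides whether the marker tests are run, real effects could also be missed. Separately, a signed-rank test cannot be applied to two independent arms as the text stands.

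**Working it through.** The plan states no error rate or power for this sequence, so there is no figure to reproduce.

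**Inputs from the documents.** Two independent arms, 40 per arm (Section 7.0), 12 cytokines (Section 6.5), two time points (Section 6.5), Bonferroni correction (Section 8).

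**Assumptions.** Two-sided alpha 0.05, so the per-cytokine level is 0.05/12 = 0.0042. Between-cytokine correlation ρ, effect sizes and pre-post correlation r are assumed as shown.

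**Gate.** Simulated at n = 40, nominal 5%, mean and SD estimated from the data:

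| Data | Ordinary KS rejects | Lilliefors rejects |
|---|---|---|
| Normal | 0.03% | 5.5% |
| Exponential | 23% | 91% |
| 30% of values at a detection limit | 19–20% | 90% |

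A calibrated gate would not settle the matter either. Across 24 arm-by-cytokine datasets, if independent, at least one fails with probability 1 − 0.95^24 = 71%, and the plan has no rule for mixed results.

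**Omnibus, by possible factor, no melatonin effect.**

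- *Arm, one cytokine at a time.* With two groups F = t². In a test dataset F = 4.159 and t² = 4.159, with p = 0.0448 for both. Kruskal-Wallis and the rank-sum test both gave p = 0.0675. The step is redundant.
- *Arm, 12 standardised cytokines pooled as independent values.* The variance of the pooled mean difference is understated by the factor 1 + 11ρ, so the null rejection rate is about 2Φ(−1.96/√(1 + 11ρ)):
  - ρ = 0.1: 1.96/√2.1 = 1.35, rate 17.6%
  - ρ = 0.3: 1.96/√4.3 = 0.95, rate 34.5%
  - ρ = 0.5: 1.96/√6.5 = 0.77, rate 44.2%

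  Simulation gave about 17%, 34% and 46%. At ρ = 0 the test is calibrated (5.3%).
- *Arm by cytokine, 24 cells.* This compares cytokines with one another. If their mean log levels differ with SD 0.25 (in within-cytokine SD units), it rejects in 94–97% of null trials; at 0.5, in 100%.
- *Arm by time, 4 cells.* Rejection is 3.5–3.7% with no time shift and 78–85% with a 0.5 SD shift shared by both arms.

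**What the final step does alone.** Twelve t-tests at 0.05/12 have familywise error 1 − (1 − 0.05/12)^12 = 4.9% if independent, and 3.7–5.5% simulated over ρ = 0.5 to 0.

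**Power if the omnibus gates the t-tests.** Take one cytokine shifted by 0.8 SD.

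- Ungated: noncentrality 0.8 × √(40/2) = 3.58 against a critical t of 2.95 (78 df) gives about 73% power.
- Requiring a significant pooled ANOVA first reduces this to about 33–36% at ρ = 0.3 to 0.5 (simulated).
- Adjusting for baseline, without gate or omnibus, multiplies the residual SD by √(1 − r²). For r = 0.3 the noncentrality is 3.58/0.954 = 3.75 (78% power). For r = 0.7 it is 3.58/0.714 = 5.01 (98%).

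**Signed-rank.** This test needs pairs. Melatonin and placebo patients are not paired, and the two-arm rank test is the rank-sum.

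**The case against.** The strongest defence is that the plan names only one grouping, by treatment. On the natural reading the ANOVA is run per cytokine with arm as the factor, and it is then valid and merely redundant. Nothing says that 12 analytes are stacked or that cytokine is a factor. This stands: the high false-positive rates belong to readings that the text permits but does not state.

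Second, claims about named markers come from the Bonferroni step. Even under the pooled reading, a significant omnibus together with at least one significant Bonferroni t-test occurs in only 0.7–4.4% of null trials for ρ from 0 to 0.5. This also stands. What remains is a global claim with no marker identified, in 15–41% of null trials at ρ = 0.1 to 0.5.

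Third, a reader might infer that a weak normality gate makes the t-tests invalid. That is not supported. At 40 per arm the two-sample t-test's type I error was 4.6–5.0% for exponential, heavy-tailed (t, 3 df) and detection-limited data, and 0.30–0.43% at the 0.42% level. The gate criticism also assumes the ordinary KS test, whereas a Lilliefors version would have about the right size.

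Fourth, the signed-rank test could be meant for baseline against six months within patients. That would be a valid paired test, but of change within an arm, not of melatonin against placebo.

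**Conclusion.** The point holds as one of redundancy and under-specification, with one misnamed test. The gate, if ordinary KS, does not usefully choose between branches. The omnibus step either duplicates the marker test or, under readings left open, gives an unreliable global statement and costs power if it acts as a gate. None of the readings tried gives a valid test of any melatonin effect that the Bonferroni tests do not already provide.

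A reader might go further and conclude that the substudy will falsely declare particular cytokines affected, or that the trial's primary result is in doubt. The documents support neither. Familywise error for named markers in the t-test branch is near 5%, the substudy is labelled exploratory, and the phase III primary analysis is a separate chi-square test. The item is therefore minor to moderate.

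The rates quoted depend on the assumed alpha, correlations, spreads and effect size. The equality F = t² and the signed-rank mismatch do not.

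**What to change.** Delete the KS gate and the ANOVA/Kruskal-Wallis step for both cytokines and flow-cytometry markers. For each marker, prespecify one model of the log six-month value on arm, adjusted for the log baseline value and the randomisation stage stratum (I/II or III/IV), with Bonferroni or Holm across the stated panel. State alpha and sidedness. If a non-parametric sensitivity analysis is kept, use the rank-sum test or a rank-based baseline-adjusted analysis in place of signed-rank. Make a global claim only from a permutation test that reassigns arm labels at patient level, keeping each patient's markers together.

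The cost is SAP wording only. The baseline and six-month samples are already scheduled, and no further patients or assays are needed.

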## NSCLC Adjuvant melatonin RCT

- e) Melatonin will increase NK cell activity of people who are ingesting this at a dose of 20mg daily.
- f) Melatonin will create a decrease in both inflammatory and anti-inflammatory cytokines including: IL4, IL6, IL10, IL12, IL15, IFN- $\alpha$ , GM-CSF, TNF- $\alpha$ , IFN- $\alpha$ , TGF- $\beta$ 1, and VEGF in people who are ingesting melatonin at a dose of 20 mg daily.

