### iii. Flow cytometry

PBMCs will be isolated from whole blood using Ficoll Paque (Stemcell). Blood lymphocytes will be analyzed for total number of NK cells using CD56 and CD3 fluorescent conjugated mAb. CD69 expression (early activation marker), IFN $\gamma$  secretion (NK cell secreted cytokine in response to activation), CD107a (cell surface degranulation marker), and Granzyme B secretion (NK cell secreted cytoxic granule) will be analyzed using specific fluorescent conjugated mAb. Events will be acquired on a Beckman Coulter CyAn and data analyzed using Kaluza software (Beckman Coulter, v1.1).

Secondary outcomes of the study include compliance, adverse events, time to recurrence and/or mortality, and scores from validated questionnaires to measure quality of life, pain, depression, anxiety, sleep, and fatigue. The following validated questionnaires will be used:

Questionnaire	Acronym	Measure of
Brief Pain Inventory	BPI	Postoperative pain
Beck Depression Index	BDI	Depression
Beck Anxiety Inventory	BAI	Anxiety
Leeds Sleep Evaluation Questionnaire	LSEQ	Sleep quality
Fatigue Symptom Inventory	FSI	Fatigue
Quality of Life in Cancer Patients	EORTC QLQ-C30	Quality of life
Quality of life in Lung Cancer Patients	EORTC QLQ-LC13	Quality of life specific in lung cancer patients

Note: the entire battery of questionnaires listed above will be administered at the Ottawa site at Baseline, 1 and 2 years. Only the Pain and Sleep questionnaires will be administered at 3 week, 3, 6, 9, and 18 months. At multicentre sites, the Sleep, Fatigue, QLQ-LC13 and QLQ-C30 questionnaires will be administered at Baseline, 1 and 2 years, and only the Sleep questionnaire at 3 week, 3, 6, 9, and 18 months.

Every document provided to the patients will be available in both English and French depending on language of preference. This also applies to the questionnaires, and licenses for each of them in both official languages have been obtained. Each of the questionnaires has been validated in both English and French.

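### The cytokine and flow-cytometry tests use single-step Bonferroni where Holm's step-down would give the same error control and never reject fewer markers

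*Combined protocol and SAP*

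**What the plan says.** Section 8, Phase II substudy analysis, *Cytokine array*, log-transforms the measurements, checks normality and runs an omnibus analysis of variance, "followed by a t-test corrected for multiple hypothesis testing (bonferroni) to identify which are significantly affected by melatonin treatment". If normality fails, a Kruskal–Wallis step and a Wilcoxon test replace these, again with Bonferroni.

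Under *Flow cytometry* in the same section, "Statistical analysis will be similar to that implemented in the cytokine analysis", and Bonferroni is again named on both branches. The method therefore appears four times. No step-down procedure is mentioned anywhere. No significance level, sidedness or list of tests forming a family is given for these comparisons.

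Four other places bear on the point:

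- Section 6.5, *ii. Cytokine array*, lists 12 analytes ("Includes IL2, IL4, IL6, IL10, IL12, IL15" and six more).
- Section 3, hypothesis (f): "Melatonin will create a decrease in both inflammatory and anti-inflammatory cytokines". It has 11 entries, 10 of them distinct because IFN-α appears twice. IL2 and IFN-γ are not named.
- Section 2.1 places the marker work under the primary objectives, but as an aim to explore. Section 7.0 calls the substudy an exploratory pilot.
- Section 7.0 plans the substudy "with 40 patients in each group".

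**The concern.** Single-step Bonferroni holds every cytokine to the threshold needed if all 12 null hypotheses were true. Hypothesis (f) expects the opposite: at least 10 of the 12 to be false. Single-step correction wastes most in that situation. These tests are meant to identify which markers respond, so any loss appears as individual cytokines missed. With 40 patients per arm, power that costs no extra patients or assays is worth having.

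**Working it through.** **The plan's own figure.** The only power statement for the substudy (Section 7.0) is that 80 subjects suffice for a 30% shift in NK cell activity. It gives no SD, level or power, so it cannot be reproduced. Back-solving the two-means formula with 40 per arm and two-sided 5%:

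- 80% power: d = (1.960 + 0.842) × √(2/40) = 0.63 SD, so a 30% shift implies an SD of about 30/0.626 = 48% of the mean.
- 90% power: d = (1.960 + 1.282) × √(2/40) = 0.725 SD, implying an SD of about 41% of the mean.

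This is why 0.63 SD is one of the scenarios below. No figure of this kind exists for any cytokine.

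**Inputs.** From the documents: 12 cytokines, 40 per arm, and 10 cytokines expected to move. The flow family is five by my count of Section 6.5, *iii. Flow cytometry*: NK number, CD69, IFN-γ, CD107a and Granzyme B. My assumptions: family-wise 5% two-sided, equal correlation of 0.3 between markers, effects of 0.3 to 0.8 SD, and normal data.

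**The two rules.** With m tests, Bonferroni rejects when p ≤ 0.05/m. For m = 12 that is 0.00417. Holm orders the p-values and compares the i-th smallest with 0.05/(m − i + 1), that is 0.05/12, 0.05/11 (0.00455), and so on up to 0.05, stopping at the first failure. No Holm threshold is below 0.05/12, so Holm rejects everything Bonferroni rejects. The first threshold is the same for both, so the chance of declaring at least one marker is identical.

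**Bonferroni power, direct calculation.** Two-sample t-test, 78 degrees of freedom, critical value 2.952 at 0.05/12, non-centrality d × √(40/2):

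- d = 0.8: non-centrality 3.58, power 73%.
- d = 0.63: non-centrality 2.82, power 45%.
- d = 0.5: non-centrality 2.24, power 25%.
- d = 0.4: non-centrality 1.79, power 13%.

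**Bonferroni against Holm.** Simulated two-sample t-tests, at least 6,000 substudies per setting, correlation 0.3; average power per truly shifted marker:

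| Setting | Bonferroni | Holm |
|---|---|---|
| 10 of 12 shifted, 0.8 SD | 73% | 82% |
| 10 of 12 shifted, 0.63 SD | 45% | 53% |
| 10 of 12 shifted, 0.5 SD | 25% | 28% |
| 10 of 12 shifted, 0.4 SD | 13% | 15% |
| 10 of 12 shifted, 0.3 SD | 6.0% | 6.5% |
| 10 of 12, unequal effects 0.1–0.8 SD | 27% | 29% |
| 6 of 12 shifted, 0.8 SD | 73% | 77% |
| 3 of 12 shifted, 0.8 SD | about 74% | 75% |
| 5 of 5 flow markers, 0.63 SD | 57% | 68% |

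In numbers of cytokines, the gain is 10 × (0.82 − 0.73) = 0.9 at 0.8 SD, 10 × (0.15 − 0.13) = 0.2 at 0.4 SD, and 10 × (0.29 − 0.27) = 0.2 with unequal effects. Correlation matters little to average power: over 0 to 0.6, the 0.8 SD result stays at 73–74% against 82–83%.

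**Error control.** With all 12 nulls true, the two rules gave the same simulated family-wise error: 5.4%, 4.4% and 3.6% at correlations 0, 0.3 and 0.6, with simulation error of about 0.3 points. With 10 of 12 shifted, Holm's was at most 4.8%. Bonferroni's was about 0.8% at 0.8 SD and correlation 0.3, as expected with two true nulls left (2 × 0.05/12 = 0.83%). The unused part of the 5% is what Holm recovers.

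**The case against.** The strongest reply is that nothing here is wrong. Bonferroni protects against false positives, the substudy is exploratory, and preferring another valid method is a refinement. That stands. A reader might infer that the present plan makes its marker findings unreliable or weakens the trial's main result. The documents support neither reading: the two-year composite outcome has its own chi-square test, and the NK cytotoxicity assay is analysed separately without Bonferroni.

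A second objection is that the larger gains need about ten cytokines all shifting by roughly 0.6 to 0.8 SD. That also stands. A reader might take the 9-point gain at 0.8 SD as what the plan loses, but hypothesis (f) predicts direction only, and the documents give no cytokine effect size, SD or correlation. At 0.4 SD or below, or with unequal effects, the gain is about 2 points or less.

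Third, bare t-tests are not the whole written procedure. The normality check, the omnibus step and the non-parametric branch were not modelled, and the text does not make clear whether the omnibus test is run per cytokine or across them. The gain realised under the full procedure is therefore unknown. That Holm rejects no fewer markers wherever it replaces Bonferroni needs no such modelling.

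Fourth, Bonferroni yields simple simultaneous confidence intervals and Holm has no equally simple counterpart. This is a true cost, but a small one, because these sections plan no such intervals.

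Finally, hypothesis (f) concerns cytokines only. For the flow markers the ordering of the two methods still holds, but the assumption that all five move is mine.

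**Conclusion.** The point holds as a modest, avoidable loss of efficiency. That Holm gives the same family-wise control under any dependence and never rejects fewer markers is a mathematical fact. The size is conditional on a two-sided 5% level, 40 per arm, correlation 0.3, 10 of 12 cytokines shifted and no omnibus step. On those terms the gain runs from about 9 points per shifted cytokine at 0.8 SD to almost nothing at 0.3 SD. If the repeated IFN-α in hypothesis (f) was meant as IFN-γ, 11 of 12 are expected to move and the gain at about 0.63 to 0.8 SD is about 8 to 12 points. If only three move, it is about 1 point at 0.8 SD.

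The 0.05/12 threshold is also an inference, since the plan states neither its level nor its families. Low priority.

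**What to change.** In Section 8, replace Bonferroni with Holm's step-down in all four places: the parametric and non-parametric branches of both *Cytokine array* and *Flow cytometry*. Changing only the t-test clauses would leave the two branches with different corrections. In the same edit, state a two-sided 5% family-wise level and define two separate families: the 12 cytokines and the listed flow-cytometry markers. Correct the repeated IFN-α in hypothesis (f) so that the number of cytokines expected to move is clear.

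The cost is a few words of text, with no extra patients, assays or data. The one thing given up is the easy matching simultaneous intervals; if these are wanted, say how they will be obtained. The edit does not repair a separate and more serious fault in the same paragraphs: the Wilcoxon signed-rank test is a paired test, and it is named there for comparing two independent groups.

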## 2. Study Objectives

### 2.1 Primary Objectives

1. To determine the effectiveness of adjuvant melatonin as compared to placebo in the prevention of cancer recurrence and mortality two years after surgical resection of NSCLC.
2. To explore the effect of melatonin on promising biological markers within participants enrolled in the larger clinical trial. These markers include the most promising assays that address areas in which melatonin may act against cancer. The assays include NK cell function and cytokine levels. In addition to addressing the very important issue of mechanism of action, the additional 80 participants will further contribute to the power of the phase III trial.

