## 4. Study Design

The study is a two-arm, randomized, placebo-controlled, blinded trial among 640 subjects who have been diagnosed with NSCLC and are scheduled for surgical resection. Of these 640 patients 80 patients at the Ottawa Hospital will be included in the biomarker sub-study. Patients will be recruited into the main trial at the Ottawa Hospital as well as other centers across Canada.

**NOTE: Past the two year follow up (until a maximum of five years), patients will be followed for recurrence date and/or date of death (using medical records, patient follow-up, and family follow-up). No questionnaires will be given past the 2-year follow up.**

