#### **6.4 Interventions**

Patients who appear to meet eligibility criteria will be approached and asked to consent to the trial by the research coordinator. After eligibility criteria have been confirmed by the investigator or medically qualified delegate patients will be randomized using a centralized system at The Ottawa Hospital to either active melatonin group or placebo. Randomization will be stratified according to cancer staging (I/II vs. III/IV). Allocation bias will be prevented by using a randomization table with variable blocks of 4 and 6. Only the Pharmacy Research Technician at the Ottawa Hospital can see the randomization table and treatment assignments.

Patients, physicians, and the research coordinator will be kept strictly blinded as to individual group allocation and treatment. The intervention, active or placebo, will be given to participants in opaque bottles with the patient study code clearly written on the corresponding container. The clinical trial pharmacist at the coordinating site will be responsible for the coding and container labeling of all containers. Instructions for taking the intervention will be identical for both control and melatonin groups. The research coordinator will be responsible for the dispensing of the pills (both active and placebo).

Melatonin or placebo will be provided to patients either on the day of discharge or up to 60 days post-operative from the hospital. In the phase II substudy, participants will only be given the intervention four weeks following surgery. This wait period is to reduce the confounding effect of the surgery on the surrogate measures we are testing. Patients will be responsible for taking their doses and will be required to report any missed doses to the research coordinator. To ensure optimal compliance, the research coordinator will telephone each patient once a week for two weeks at the beginning of the trial. Telephone calls will then be made as needed until the completion of one year while the patient is on the study drug.

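### If normality fails, the biomarker sub-study names a paired test (Wilcoxon signed-rank) to compare two independent arms; it should be the rank-sum test, with the analysed value stated

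*Combined protocol and SAP*

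**What the plan says.** The trial has two parallel arms: "The study is a two-arm, randomized, placebo-controlled, blinded trial among 640 subjects". On allocation, section 6.4 says: "Randomization will be stratified according to cancer staging (I/II vs. III/IV"), using blocks of 4 and 6. It mentions neither matching of patients between arms nor stratification by site or sub-study.

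Section 6.5 (surrogate tests for the phase II substudy) draws blood twice: four weeks after surgery before treatment starts, and six months into treatment.

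In section 8, the Cytokine array paragraph says "patients will be divided into two cohorts; those receiving melatonin and those receiving placebo treatment". Log-transformed values are checked for normality with a KS test, and the plan then branches:

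- **Normal:** one-way ANOVA, then a Bonferroni-corrected t-test. Paired or two-sample is not stated.
- **Not normal:** Kruskal-Wallis, "followed by a Wilcoxon signed-rank test corrected for multiple hypothesis testing (bonferroni) to identify which are significantly affected by melatonin treatment".

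The Flow cytometry paragraph uses the same sequence for NK-cell markers. None of the sub-study analysis paragraphs mentions the baseline sample.

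On status, section 7.0 says "An exploratory pilot analysis of 80 subjects will provide information on what is occurring physiologically", whereas section 2.1 lists the biomarkers as a primary objective: "To explore the effect of melatonin on promising biological markers within participants enrolled in the larger clinical trial".

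**The concern.** The signed-rank test works on differences within pairs, or on a single sample. Here the contrast is between two groups of different people, and the Kruskal-Wallis test just before it is an independent-groups test. An analyst who follows the text must decide which melatonin patient is set against which placebo patient, and the p-value depends on that choice. If the arms differ in size, some patients have no partner.

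Two analysts could therefore name different markers as affected by melatonin from the same data, and a pairing could be chosen after the results are seen. A second, smaller gap leaves room for the same thing in both branches: the plan does not say whether the six-month level, the change or a baseline-adjusted level is tested.

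**Working it through.** The plan gives no figure for these tests to reproduce. The error follows from setting the paragraphs side by side, and the calculations only gauge its size.

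**Inputs from the documents.** 40 patients per arm (section 7.0). Twelve cytokines, counting the full list in section 6.5 ii that begins "Includes IL2, IL4, IL6, IL10, IL12, IL15". Per-test alpha if those 12 form the Bonferroni family: 0.05/12 = 0.0042.

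**Assumed inputs.** Normal data unless stated, effect sizes in SD units, and the correlation between baseline and six-month values.

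**1. Arbitrary pairing, equal arms, alpha 0.05/12.** Each simulated dataset was paired at random in two ways. Ranges are across repeated sets of runs.

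| True effect (SD) | Datasets where the two pairings disagree on significance |
|---|---|
| 0.5 | 9% |
| 0.63 | 12–13% |
| 0.7 | 12–13% |
| 0.85 | 9–11% |
| 1.0 | 5–6% |

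Type I error is 0.3–0.4% against a nominal 0.42% (4.1–4.9% at alpha 0.05). Power at 0.85 SD is 73–75%, against 76–77% for rank-sum. Error rates are therefore close to those of the right test; the answer for a given dataset is not fixed.

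As an illustration, one skewed (lognormal) dataset with 40 per arm gave a rank-sum p of 0.013. Over 5,000 random pairings, the signed-rank p ran from 0.0005 to 0.146.

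**2. Unequal arms.** The test cannot be run on, say, 40 against 38. Suppose the 80 come from the main randomization table. Simulating blocks of 4 and 6 in two stage strata (70% or 85% stage I/II assumed), with 80 drawn at random from pools of 100 to 640, gives exactly 40/40 in 9–20% of runs. The mean difference between arms is 3.2–6.7 patients before any dropout. The documents do not say how sub-study allocation was handled beyond section 6.4.

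**3. Precision left unused.** From the two-sample t-test power function with 40 per arm, the effect detectable with 80% power is 0.634 SD at 0.05 and 0.851 SD at 0.05/12. Adjusting for baseline multiplies this by √(1 − ρ²):

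- ρ = 0.3: 0.851 × √0.91 = 0.81
- ρ = 0.5: 0.851 × √0.75 = 0.74 (at alpha 0.05, 0.634 × √0.75 = 0.55)
- ρ = 0.7: 0.851 × √0.51 = 0.61

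With equal SDs at both times, a change score has variance 2(1 − ρ) relative to the six-month value, so it gains precision only if ρ exceeds 0.5. Omitting baseline costs precision but does not bias a randomized six-month comparison.

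**The case against.** **It is probably a naming slip.** With two groups, Kruskal-Wallis on a single marker is already equivalent to the two-sided rank-sum test, so a valid comparison is in the plan. That is fair, and it is why the fix is small. But the plan assigns the identification of affected markers to the later test, and that is the wrong one.

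**The branch may seldom be reached.** An uncorrected KS test with fitted mean and SD at n = 40 (assumed, since the variant is not stated) rejects in 0% of normal datasets, 5–8% of moderately skewed or heavy-tailed ones, and 20% when 30% of values sit at a detection limit. A corrected KS test, or a rule that any failing dataset triggers the branch, would raise this. The disagreement rates above are conditional on entering the branch.

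**Unequal arms would expose the error.** Software would usually stop, so silent mispairing and unequal arms are alternative problems and should not be added together. This stands.

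**Within-patient change may have been meant.** The documents do not say so, and testing change within the melatonin arm is not a comparison with placebo. With no drug effect and drift common to both arms of 0.5 SD of the change, such a test at 0.05/12 is positive in 53% of datasets. That falls to about 2.5% if a per-marker between-arm Kruskal-Wallis test at 0.05 must pass first. The conclusion does not rest on this reading.

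**The rest is preference or labelling.** Section 6.5 calls the six-month draw the end point, which hints at the analysed value. ANCOVA is a preference. Both points are accepted: the baseline issue is a secondary gap and adjustment is optional.

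**Conclusion.** The concern holds. In both the cytokine and flow-cytometry paragraphs, the non-normal branch names a paired test for independent groups, and nothing in the documents supplies a pairing. This follows from the text and does not depend on the simulation assumptions.

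The consequence is moderate. At the assumed effects, an arbitrary choice changes whether a marker is called significant in roughly one dataset in ten, and patients are lost if the arms are unequal. False positives are not inflated and average power is about the same. The fault touches only the non-normal branch of an exploratory sub-study and leaves the two-year recurrence and mortality analysis alone. It should still be corrected, because the biomarkers sit under the primary objectives and the correction is almost free.

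**What to change.** **Minimum, in both the Cytokine array and Flow cytometry paragraphs of section 8:**

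- Replace the signed-rank test with the Wilcoxon rank-sum (Mann-Whitney) test comparing the melatonin and placebo arms.
- State that the t-test is unpaired.
- State the analysed quantity: six-month value, change, or baseline-adjusted value.
- Keep Bonferroni and give the divisor. Section 6.5 ii lists 12 cytokines, whereas hypothesis (f) in section 3 has 11 entries, 10 of them distinct, so the family needs to be named. Count flow markers separately.

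The two-group ANOVA or Kruskal-Wallis step, run per marker, is redundant but harmless.

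**Optional, for precision:** in the normal branch, ANCOVA of the log six-month value on log baseline, arm and stage stratum. In the non-normal branch, a rank-sum test on residuals from regressing ranked six-month on ranked baseline values. If this is adopted, say that normality is judged on model residuals, whether stage enters both branches, and how missing six-month samples are handled.

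**Cost:** analysis wording only, to be settled before unblinding. The baseline sample is already scheduled, and no new data or patients are needed.
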